### *Exploratory Endpoints*

Exploratory endpoints have been specified for patients with infection suitable for outpatient antibiotic therapy (OPAT) management. These endpoints are collected for 16 weeks following randomization by review of VUMC's electronic medical record:

- a) New, persistent, or recurrent infection: defined by positive culture and/or change in antibiotic regimen
- b) Completion of antibiotic therapy
- c) Days from negative blood culture (i.e., blood draw date) to first hospital discharge

### *Implementation Endpoints*

- a) Acceptance of Bridge Clinic as a bridging provider, defined by being physically checked in for at least 1 visit with the Bridge Clinic within 16 weeks of follow up.
- b) Reasons for ineligibility among participants screened, specifically:
  - o Absence of a qualifying OUD
  - o Previously linked with a MOUD provider either prior to or during the current visit?
  - o ACT determines the participant does not qualify

### *Fidelity Endpoint*

- a) Cross-over, defined as when a patient randomized to usual care is offered the Bridge Clinic, or when a patient is randomized to Bridge Clinic but is only offered usual care, at the time of discharge from the inpatient stay.

### **Analysis dataset**

The analysis for the trial will use an intent-to-treat approach to answer the effectiveness question posed. That is, participants will be evaluated by treatment group as assigned regardless of what was delivered. All eligible participants will be included. There is no plan to restrict the analysis to a per protocol set.

### **Statistical Approach**

Our initial analysis will be descriptive in nature, summarizing information that characterizes the cohort and the outcomes. Then, we will proceed with inferential analysis to answer the main study question. Then, we will compare the secondary endpoints between study groups.

### *Descriptive Analysis*

To characterize the study sample, baseline demographic and clinical data will be described overall and by group. Categorical variables will be described using frequencies and proportions, and continuous variables will be described using means and standard deviations, as well as medians and interquartile ranges. Missingness will be reported for each variable. Graphical summaries using box plots, violin plots, and/or histograms may be used to describe the data graphically. At a minimum, the following variables will be described at time of enrollment:

- Age (years)
- Gender (male, female, unknown)
- Race (African American, Asian/Pacific Islander, Caucasian, Multiple, Native American, Other, Unknown)
- Ethnicity (Hispanic, Non-Hispanic, Unknown)
- Census tract area deprivation index

We will describe all of the outcome variables overall and grouped by study arm using the same approach as for the demographic data. Summary statistics and graphical representations may be displayed, and missingness will be reported for each variable.

No statistical comparisons between groups will be done for this descriptive analysis.

### *Main Analysis*

The primary outcome variable (hospital index length of stay) will be compared between groups using an adjusted generalized linear model. Since the data are positive and may be skewed, like a gamma distribution, we may use a negative inverse link function, a proportional odds model, or transform the data.

In this analysis, group assignment is the main predictor variable. For drawing conclusions about the effect of the Bridge clinic, a critical p-value of 0.05 for the effect of treatment group assignment on the primary outcome will be used. The model will be adjusted for age, race, ethnicity, and area deprivation index. The influence of continuous variables will be assessed using restricted cubic splines with a minimum of three knots. We do not expect missingness in our primary outcome. If there are missing covariates, cases will not be excluded; we will use multiple imputation with predictive mean matching for missingness in adjusting covariates.

Secondary and implementation outcomes will be compared between study groups using adjusted generalized linear models, just as for the primary endpoint. Binary endpoints will use a logit link function. For counts, such as number of medication refills, either a zero-inflated Poisson or a negative binomial model will be fit.

Exploratory outcomes for OPAT patients will not be compared between study groups but will be reported by study group.

There may be missingness in secondary or implementation outcomes. If there are missing outcomes, these may be imputed if they occur in less than 5% of cases. Otherwise, the cohort for which the outcome is available will be described, along with the results of the model evaluating treatment effects in this cohort. All model results will be summarized with point estimates and 95% confidence intervals (CIs), which will be emphasized over p-values when reporting the results for secondary and implementation outcomes. No adjustments for multiplicity will be made.

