Due to COVID and the resulting changes in patient flow, we will temporarily suspend eligibility for the trial for OPAT patients as of December 3rd, 2020.

Principal Investigator: [name]

Version Date: April 7, 2022

Study Protocol: Evaluating the Impact of the Bridge Clinic in Patients with Opioid Use Disorder

Comparators:

- Direct referral to a long-term outpatient addiction provider
- Referral to the Bridge Clinic while long-term outpatient addiction provider is located/identified

Randomization: Randomization will occur at the individual patient level. Currently, the Bridge Clinic can only accept a limited number of patients. To learn from the care provided, we propose randomizing all patients eligible for referral to Bridge Clinic in a ratio such that the Bridge Clinic is at capacity. In this way, the choice to refer is unbiased and the strength of evidence is greatly enhanced.

Consent: This study involves comparing two approaches to care: i) inpatient MAT (buprenorphine or naltrexone) with search for an outpatient MAT provider to accept the patient, or ii) inpatient MAT (buprenorphine or naltrexone) with referral to the Bridge Clinic to maintain the patient's care until a long-term outpatient MAT provider accepts the patient. Both approaches represent standard of care.

It is not practicable to answer the research question with informed consent because patients who choose to participate will necessarily differ from those who do not in substantial ways, including access to care.

We request a waiver of consent as 1) all data for the research will be obtained from the medical record, financial systems, state-mandated reporting systems, and from routine standard of care telephonic outreach to patients, 2) we are comparing usual care practices, albeit with randomization, 3) there is no additional interaction with the participant for research purposes, and 4) it is impracticable to conduct the research with consent.

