The Bridge Clinic was designed and implemented based on work completed at MGH, Boston Medical Center, Yale and UAB. The intent is to obviate the challenge that patients being considered for MAT are often not discharged until an outpatient provider willing to accept the patient has been identified, resulting in delays to discharge. By serving as a bridging provider, any delay in discharge is avoided. Moreover, the subset of patients requiring IV antibiotic therapy are often admitted for a full six-week course of treatment unless a skilled nursing facility is available, also at considerable expense to the healthcare system. For patients meeting low risk criteria, the multi-specialty Bridge Clinic is available to manage the antibiotic therapy as an outpatient. This provides further opportunities for the Bridge Clinic to broadly impact the hospital bed days dedicated to caring for this patient population while simultaneously providing access to dedicated care. While implemented clinically based on available evidence, the effectiveness of this care model in improving patient outcomes while reducing time in hospital has yet to be quantified in situ.

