10.0 Statistical Considerations

Statistical Analysis Plan:

Initially, we will characterize participants overall and grouped by study arm using descriptive statistics (e.g. means with standard deviations, medians with interquartile range, and counts with percentages, as appropriate). Data may also be described graphically. The primary analysis will compare length of index hospital stay between those offered referral to the Bridge Clinic and those not offered referral to the Bridge Clinic on an intent-to-treat basis. We will compare length of stay using a generalized linear model with group assignment as the primary predictor variable, with adjustment for important covariates. We expect to model the outcome as a continuous outcome. We may choose to use a proportional hazards model or a gamma GLM with a log-link function if the data are substantially skewed; we do not expect this based on our experience with length of stay in this patient cohort. For secondary outcomes, costs will be similarly modeled. Binary outcomes will be modeled using logistic regression, Quality of life outcomes will be modeled using a proportional odds regression. Additional analyses that we expect to perform include 'per protocol' comparisons between study groups and characterization of implementation measures.

Power and Sample Size Considerations:

We estimate 700 patients per year, or about 14 patients per week, will be eligible to participate in this study, with a capacity for approximately 3-4 new patients per week to be seen at the Bridge Clinic. We expect approximately 2/3 of patients referred to the Bridge Clinic to make their first appointment. Therefore, we will randomize patients at a rate of 1:1 to Bridge Clinic versus usual care. The randomization may be adapted if eligibility and follow up rates are different to expected. The mean length of stay for patients is currently 15 days, ranging from 3-42 and a standard deviation of about 15 days. With 700 patients in a year, allocated 1:1, we will have about 80% power to detect a 3-day reduction in length of stay. This does assume a reduced standard deviation of 10 days. If the standard deviation remains at about 15 days, the difference detectable with 80% power is 3.5 days.

Interim Analysis

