### *Differential treatment effects*

To determine whether effects of treatment on the primary endpoint depends on any of the baseline characteristics, we will test the interaction between the baseline characteristics and treatment effect in the regression model. If evidence of an interaction is observed using a threshold of  $p < 0.2$ , we will proceed to subgroup analyses. For categorical variables, endpoints will be compared between within categories. For continuous variables, we will display the partial effects plots showing how treatment effects change with the putative subgrouping variable.

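### The primary length-of-stay model omits IV-antibiotic need, a likely strong predictor of stay and plausible effect modifier; the cost is some precision and interpretability, not bias

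*SAP*

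**What the plan says.** The protocol (10.0 Statistical Considerations) promises a length-of-stay model "with adjustment for important covariates" and names none. The SAP (Main Analysis) names them: "The model will be adjusted for age, race, ethnicity, and area deprivation index". No clinical variable is among them.

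On patients needing IV antibiotics, the protocol's 2.0 Background says that "the subset of patients requiring IV antibiotic therapy are often admitted for a full six-week course of treatment unless a skilled nursing facility is available". It adds that, for those at low risk, the Bridge Clinic can manage the antibiotics on an outpatient basis. The subgroup has its own aim (Aim 4) and its own exploratory hypothesis. Section 1.0 also records that, because of COVID, "we will temporarily suspend eligibility for the trial for OPAT patients as of December 3rd, 2020".

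For effect modification, the SAP (Differential treatment effects) says "we will test the interaction between the baseline characteristics and treatment effect in the regression model", with no list of factors. The Descriptive Analysis section introduces its five demographic and deprivation variables with "At a minimum, the following variables will be described at time of enrollment". For the outpatient-antibiotic (OPAT) endpoints, the SAP says: "Exploratory outcomes for OPAT patients will not be compared between study groups but will be reported by study group". Neither the protocol's baseline data elements (6.0 Study Procedures) nor the SAP's named baseline variables include infection status.

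**The concern.** The documents tie no other baseline factor to a difference in stay of this size. The blinded re-estimate (protocol 10.0, Interim Analysis) gives an overall mean of 9 days and a geometric mean of 5.5 days. A subgroup that often stays six weeks sits far out in the tail of that distribution. Leaving its marker out of the model leaves avoidable noise in the primary estimate, including noise from chance imbalance of long-stay patients between arms.

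There is also a question of meaning. The clinic is expected to act in two ways: by removing the wait for an outpatient provider, and by moving IV therapy out of hospital. The second applies only to this subgroup. A single pooled effect averages over both, in a mix that the OPAT suspension altered. If the effects differ, a reader will want the effect in patients without the IV indication, and the plan does not promise it.

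**Working it through.** **Inputs.** From protocol 10.0: log-scale mean ln(5.5) = 1.705; log-scale SD ln(2.7) = 0.993, so variance 0.987; target reduction 1.5 days, which I read as ln(5.5/4.0) = 0.318; 168 per group; 80% power. From the SAP: critical p-value 0.05, taken as two-sided. Not in the documents, so assumed: prevalence p of the IV indication, and the log-stay difference d between patients with and without it.

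**The plan's own figure.** n per group = 2 × (1.960 + 0.842)² × 0.993² / 0.318² = 153. The stated 168 is about 10% higher, on the safe side. The difference is a separate matter and nothing below depends on it. Power at 168 per group: SE = 0.993 × √(2/168) = 0.1084; 0.318/0.1084 − 1.960 = 0.98, so power is 83.6%. This ignores any gain from the four listed covariates.

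**Gain from the omitted factor.** R² = p(1 − p)d²/0.987. Equivalent extra patients = 1/(1 − R²) − 1. Adjusted power uses SD 0.993 × √(1 − R²). The factor is assumed unrelated to the listed covariates. With d = 1.0, a stay ratio of about 2.7:

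| p | R² | Extra patients | Power at 168 per group |
|---|---|---|---|
| 2% | 0.020 | 2.0% | 84.3% |
| 5% | 0.048 | 5.1% | 85.4% |
| 10% | 0.091 | 10.0% | 86.9% |

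A one-SD chance imbalance shifts the unadjusted log effect by √(2p(1 − p)/168) × d. At p = 10% and d = 1.0 this is 0.033, or 10% of 0.318.

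**Is d = 1.0 reasonable?** Each assumption must roughly return the reported raw mean of 9 and SD of 11. Take two lognormal groups with equal log spread, overall log mean 1.705 and total log variance 0.987. Write m = 1.705 − pd and w = 0.987(1 − R²). Then the mean is exp(m + w/2)(1 − p + p·e^d) and the second moment is exp(2m + 2w)(1 − p + p·e^(2d)).

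- Single lognormal, no subgroup: mean 9.0, SD 11.7.
- d = 1.0: mean 9.0-9.1, and SD 12.0, 12.4 and 12.7 at p = 2%, 5% and 10%. Roughly compatible.
- d = ln(42/5.5) = 2.03: SD 16.7, 19.2 and 19.0. Not compatible with 11.

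The result for d = 2.03 leans on equal log spread. Suppose instead that 5% of patients all stay exactly 42 days (ln 42 = 3.738). The others' log mean is (1.705 − 0.05 × 3.738)/0.95 = 1.598, so d = 2.14 and R² = 0.0475 × 2.14²/0.987 = 0.22. The others' log variance is (0.987 − 0.218)/0.95 = 0.810, giving them a mean of 7.41 and SD of 8.27. The overall mean is 0.95 × 7.41 + 0.05 × 42 = 9.1, and the SD is √(0.95 × (7.41² + 8.27²) + 0.05 × 42² − 9.14²) = 11.0. So the reported summary does not strictly exclude a larger gain. It needs every such patient to stay the full course, and the Background says only that this happens often, and not where a skilled nursing facility is available.

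**Does omission bias the result?** A simulation on the log scale used 4,000 runs per setting, 336 patients, 1:1 allocation and the subgroup enrolled only in the first half. The average estimate was the same with and without the covariate (−0.32 in both models at p = 10%, stay ratio 4). Rejection under no effect was 4.6-5.3% across settings. The empirical SE at p = 10% and ratio 4 fell from 0.109 to 0.100. That ratio is larger than d = 1.0 implies.

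**The case against.** The strongest reply is that the planned analysis is valid as it stands. Allocation is by individual, the SAP says that the 1:1 ratio never changed, and the analysis is by intention to treat. Power is already 83.6% on the stated inputs, so extra precision is welcome but not needed. All of that stands.

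Three stronger readings are tempting, and the documents do not support them.

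- A reader might infer that the SAP's interaction tests exclude this factor. They have no list. The section speaks of baseline characteristics generally, and the Descriptive Analysis variables are a minimum that sits beside unspecified clinical data. The factor is unnamed, not excluded.
- A reader might infer that mixing patients enrolled before and after the suspension undermines the comparison. It does not: the pooled log-scale effect is a valid average over the patients enrolled. The mix affects only what that average means.
- A reader might infer that everyone enrolled after December 2020 was free of IV-antibiotic need. The suspension is called temporary, no restart or end date is given, and it covers OPAT patients. Patients who need IV antibiotics but are unsuitable for outpatient management are not obviously covered.

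It is also fair to say that the indicator is not a listed baseline element. Being able to suspend OPAT patients as a group does not prove that IV need was recorded before randomization. A status settled later could be affected by allocation and would be an unsafe covariate. Finally, reporting OPAT outcomes by arm without a test is reasonable for a small subgroup.

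**Conclusion.** The point holds as a modest, inexpensive improvement. The primary model leaves out the factor that the protocol itself links to the longest stays and to a separate mechanism. The comparison remains unbiased. On assumed prevalences of 2-10% and a log difference of 1.0, the covariate is worth about 2-10% more patients and lifts power from 83.6% to about 84-87%. If the suspension left few such patients, the gain is at or below the bottom of that range. A larger gain should not be claimed: with equal log spread it contradicts the reported SD, and otherwise it needs tight clustering near six weeks.

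The arithmetic applies to a log-transformed linear model. The SAP also allows a proportional odds model or an inverse link. Under those, adding a strong covariate changes the conditional effect being estimated as well as its precision. That is a further reason to settle the covariate before unblinding.

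**What to change.** Before unblinding:

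1. Add to the SAP's primary covariates: *infection requiring a course of IV antibiotics, documented before randomization (yes/no)*. Abstract it from medical-record entries dated before randomization, blind to arm.
2. Name this indicator as a baseline characteristic in the Differential treatment effects section.
3. Report the length-of-stay effect with 95% CI in patients without the indication, whatever the interaction p-value.
4. Label any estimate within the IV-antibiotic subgroup as descriptive, and give the numbers enrolled before and after 3 December 2020.

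The cost is one degree of freedom, a short amendment to the SAP and a small chart abstraction. Aim 4 already requires the subgroup to be identified, but the dating relative to randomization is new work. Any subgroup interval will be very wide: 2-10% of 336 is about 7 to 34 patients across both arms. If pre-randomization status cannot be established reliably, the covariate should not be used, and the SAP should say so.

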5.0 Enrollment/Randomization

Principal Investigator: [name]

Version Date: April 7, 2022

Study Protocol: Evaluating the Impact of the Bridge Clinic in Patients with Opioid Use Disorder

The Addiction Consult Team (ACT) will be notified of potentially eligible patients via an EPIC consult order or referral from the general or homeless psychiatry service. Those patients for whom an order for an addiction medicine consultation is placed will be evaluated by the ACT for MAT. If the ACT considers MAT to be clinically appropriate, the patient does not have set plans for outpatient care, and the patient has not been previously randomized in this study, they will be enrolled and randomized. All other patients will be treated with usual care without availability of referral to the Bridge Clinic.

Screening information from enrolled patients will be entered into REDCap. For patients meeting objective criteria but whom the ACT determine ineligible for MAT, the reason for not enrolling them will be collected.

Once eligibility is confirmed, the patient will be randomized to being offered referral to the Bridge Clinic or not, as described below. Randomization will occur at the individual patient level. Randomization ratio will start at 1:1 and will be updated as necessary, but no more frequently than bi-weekly, to maintain the Bridge Clinic at capacity.

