## **Introduction**

To improve care for patients with opioid use disorder (OUD), Vanderbilt has implemented an Addiction Consult Team (ACT) and a Bridge Clinic. The primary purpose of the Bridge Clinic is to facilitate discharge for inpatients who are being considered for medications for OUD (MOUD). Specifically, the Bridge Clinic provides patients with temporary access to treatment at an outpatient clinic while they are waiting to be accepted into a long-term clinic. This document describes the statistical analysis plan for a pragmatic, single center, randomized, controlled trial designed to evaluate the impact of the Bridge Clinic on improving care for patients with active OUD. This document has been prepared prior to final data collection and unblinding. Because inpatient providers may delay discharge for patients with OUD who lack a source of outpatient care for MOUD, it is hypothesized that OUD patients referred to the Bridge Clinic will have a decreased overall length of stay, will follow up with their Bridge Clinic provider, and will have a reduction in overall costs for care.

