### *Randomization:*

Randomization occurs at the individual patient level. The Bridge Clinic can only accept a limited number of patients, so eligible patients will be randomized in a ratio so that the Bridge Clinic is at capacity. To start, the ratio will be 1:1, and can be updated as often as bi-weekly to maintain the Bridge Clinic capacity. There has been no indication or need to change the ratio during the study.

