### *Sample Size Considerations:*

We estimated about 700 patients per year would be eligible for this study, with a capacity for about 3-4 new patients a week to be seen at the Bridge Clinic. We expected about 2/3 of patients referred to the Bridge Clinic to make their first appointment. The mean length of stay was 15 days with a standard deviation of about 15 days. Assuming a reduced standard deviation of 10 days, with 700 patients a year and a 1:1 randomization ratio, we would have 80% power to detect a 3-day reduction in length of stay. If the standard deviation remains at 15 days, we would have 80% power to detect a 3.5-day reduction in length of stay. Due to COVID-19, enrollment was lower than expected and hospital inpatient experiences differed from historical data. Midway through the recruitment period, the overall, ungrouped distribution of length of stay was re-estimated based on participant experience. Based on the revised assumptions, to detect a 1.5-day

reduction in length of stay and assuming the observed common standard deviation is a good estimate, about 336 patients (168 per group) is needed to have 80% power.

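### The primary model has no term for date of randomization, although case mix and setting shifted during the trial and the allocation ratio may still change; at constant 1:1 this costs a little precision and causes no bias

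*SAP*

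**What the plan says.** The protocol (10.0 Statistical Considerations) plans a generalized linear model for index length of stay "with adjustment for important covariates", without naming them. The SAP (Main Analysis) names four: "The model will be adjusted for age, race, ethnicity, and area deprivation index". It says that secondary and implementation outcomes are modelled in the same way. No form of calendar time appears anywhere in the analysis.

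Three parts of the documents bear on time:

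- **Case mix.** The protocol's Study Summary temporarily suspends eligibility of OPAT patients from December 3, 2020. The protocol Background says that patients who need IV antibiotics are often kept in hospital for the whole six-week course.
- **Setting.** The SAP (Sample Size Considerations) says that, because of COVID-19, "enrollment was lower than expected and hospital inpatient experiences differed from historical data".
- **Allocation.** Protocol 5.0: "Randomization ratio will start at 1:1 and will be updated as necessary, but no more frequently than bi-weekly". The SAP (Randomization) repeats that the ratio "can be updated as often as bi-weekly to maintain the Bridge Clinic capacity", then adds: "There has been no indication or need to change the ratio during the study". The SAP Introduction says: "This document has been prepared prior to final data collection and unblinding". The rule therefore remains open for the patients still to be enrolled.

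Gender is on the SAP's list of baseline variables (Descriptive Analysis) but not in the model. Differential Treatment Effects plans interaction tests between treatment and the baseline characteristics, without listing which.

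**The concern.** Removing a long-stay group partway through enrollment, and possibly readmitting it later, changes the expected length of stay by date of entry. So may the pandemic. None of the four covariates carries that information. Date of randomization should be available for every patient, since the 16-week follow-up runs from it.

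Two things are at stake. With constant allocation, variance that a date term could explain stays in the residual, and the primary test loses some power. If the ratio is changed, the arms will differ in their mix of early and late patients, and a model without time will credit part of any trend to the Bridge Clinic or to usual care.

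Gender is a smaller matter of consistency. If it is one of the characteristics tested for interaction, that test needs a model with a gender main effect, and none is specified.

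**Working it through.** **Inputs.** Log-scale mean ln(5.5) and SD ln(2.7) = 0.993, and 168 per group (protocol, Interim Analysis); critical p-value 0.05 (SAP, Main Analysis), taken as two-sided. Assumption: the 1.5-day reduction is read as 5.5 to 4.0 days, so the target is ln(5.5/4.0) = 0.318 on the log scale.

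**The plan's own figure.** n per group = 2 × (1.960 + 0.842)² × 0.993² / 0.318² = 153, or 306 in total, against the stated 168 and 336. The documents do not say how 1.5 days was placed on the log scale or whether the number was inflated. This gap is a separate matter. At 168 per group, power under this reading is 83.6%.

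**Allocation constant at 1:1.** If calendar time explains a share R² of the variance, the residual SD becomes 0.993 × √(1 − R²). Power at 168 per group:

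| R² (assumed) | Power | Gain over 83.6% |
|---|---|---|
| 0.02 | 84.3% | 0.7 points |
| 0.05 | 85.4% | 1.8 points |
| 0.10 | 87.2% | 3.6 points |

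To place this range: a step by factor f between two equal halves gives R² = 0.25 × (ln f)² / 0.993². That is 0.066 for f = 0.6 and 0.013 for f = 0.8. Bias is zero. In a simulation of 336 patients (4,000 runs), type I error was 5.4% without and 5.3% with a period term at f = 0.6, and 5.0% and 5.1% at f = 0.8.

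**Ratio changed (hypothetical).** Take two equal halves, a share p₁ then p₂ allocated to the Bridge Clinic, and a log shift s = ln f between halves:

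bias = s × [p₂/(p₁ + p₂) − (1 − p₂)/(2 − p₁ − p₂)]

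For f = 0.6, s = −0.511:

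- 1:1 then 1:2: −0.511 × (0.400 − 0.571) = +0.088, about 0.5 day at 5.5 days, or 28% of 0.318
- 1:1 then 1:3: −0.511 × (0.333 − 0.600) = +0.136, about 0.8 day, or 43% of 0.318

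For f = 0.8 the values are 0.038 and 0.060 (12% and 19%). A positive sign works against the Bridge Clinic. A move to 2:1 in its favour reverses the sign: −0.088 at f = 0.6.

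Simulated type I error without a period term was 13.7% (1:2) and 23.8% (1:3) at f = 0.6, and 6.8% and 8.8% at f = 0.8. For 1:2 at f = 0.6, power was 56% without the term and 83% with it.

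**Late change.** If only the last 10% of patients (assumed) moved to 1:3, with the same 0.6-fold fall at that point: Bridge share late = 0.025/0.475 = 0.053; control share late = 0.075/0.525 = 0.143; bias = −0.511 × (0.053 − 0.143) = +0.046, or 14% of the target.

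**The case against.** The strongest reply is that the trial as described has no validity problem. The SAP reports that the ratio has not needed changing, and at a constant ratio date of entry is independent of arm. That stands. The SAP also reports the midway sample-size review as done, so a halfway switch is already excluded; only a later and less harmful one remains possible. The direction is uncertain too. The protocol's example of 1:3 applies when eligible patients outnumber clinic slots, whereas lower enrollment would push the ratio the other way.

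A reader might take the planned mean of 15 days and the observed 9 days as drift within the trial. On raw days, with halves of 168 and a change from 1:1 to 1:3, that gives (84×15 + 42×9)/126 = 13.0 for the Bridge Clinic and (84×15 + 126×9)/210 = 11.4 for control. The difference of 1.6 days is as large as the 1.5-day target. The documents do not support this reading. Fifteen days is a pre-trial figure. Nine days is the pooled mean of all patients enrolled by midway, so the early patients did not average 15. The target was also sized on the log scale, where even this extreme step reaches less than half of it. The factor 0.6 (9/15) serves above only as an outer bound.

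It is also fair to say that no document shows gender to predict length of stay, and that leaving a covariate out of a randomized comparison is not an error. What survives is the documented change in OPAT eligibility, the open ratio rule, and the unspecified model for a gender interaction.

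**Conclusion.** This is a minor point that is cheap to settle. At constant 1:1 allocation the primary comparison is unbiased and its type I error holds at about 5%. The omission then costs about 1 to 4 points of power for an assumed R² of 2% to 10%. If the ratio is changed while length of stay is trending, the omission becomes a source of bias: up to about 0.09 to 0.14 on the log scale in an extreme case that the SAP's own statement already excludes, and about 0.05 for the late change worked above.

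A reader might infer that the primary result is confounded by the pandemic, or that one ratio change could create or hide the whole target effect. Neither follows from the documents. The figures rest on a log-scale analysis, which the SAP permits but does not fix, on reading 1.5 days as 5.5 to 4.0, and on assumed trends. The gender term is justified by consistency alone.

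**What to change.** Before unblinding, amend the SAP's Main Analysis:

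1. Add date of randomization to the primary model as a restricted cubic spline with three knots.
2. Add gender as a main effect in the primary model, so that a treatment-by-gender interaction has a specified model.
3. State that, if the allocation ratio is ever changed, allocation period enters as a factor in all between-group models.
4. State that items 1 and 2 apply to the primary model only. Otherwise the wording that models secondary outcomes like the primary would carry them into models with few events, such as death and overdose.

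The cost is a few lines of SAP text and three to four degrees of freedom out of 336 patients: two for the spline and one or two for gender, depending on whether the unknown category is used. The same terms added after unblinding would look data-driven.
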